Study: Proper identification of ribs underlying the rhomboid major and trapezius muscles using palpation.

Dated 8/19/19, originally created 6/18/2015

NCT number: NCT04066166

Principle Investigator: [name]

Co-Investigators: [name], DO
[name]

Project summary: This study will determine the accuracy of medical practitioners in locating the posterior ribs underlying the rhomboid major and trapezius muscles in individuals of different Body mass indices.

Project description:

Rationale:

Cervical pain with associated myofascial trigger points is a common musculoskeletal issue with prevalence ranging from 30-85% (Gerwin 1995, Skootsky 1989). Treatment options for myofascial trigger points include both non-invasive and invasive treatments. Non-invasive treatments include deep pressure, massage, heat, TENS, and spray and stretch (de las penas 2005, Hou 2002). More aggressive, invasive treatment options include dry needling, anesthetic injection, or Botulinum toxin A injections (Liu 2015, Cummings 2001, Ho 2006, Scott 2009). Complications associated with dry needling are rare but include infection, bleeding, pain, epidural hematoma, and pneumothorax (Conway 2013, Cummings 2014, Ding 2013, He 2012, Juss 2008, Lee 2011, Karavis 2015, McCutcheon 2011).

Pneumothorax, which is a collapse of the lung, can result from trigger point injections to the muscles in close proximity to the ribs such as rhomboid major, rhomboid minor, trapezius, diaphragm, shoulder muscles, and neck muscles, where the needle is penetrated too deep and passes the pleura. Though the reported incidence of pneumothorax has been reported to be around 1 in 100,000 (Witt 2009, Melchart 2004), there is some thought that pneumothoraces may be underreported for two reasons - patients may have a subclinical pneumothorax or fail to report to their practitioner about shortness of breath or dry cough.

The rhomboid major muscle originates on the spinous processes of the T2-T5 vertebra and inserts on the medial border of the scapula. There has been a study to address the appropriate depth for needle insertion when dry needling or injecting the rhomboid major (Seol 2014). To our knowledge, there have been no studies to investigate a practitioner's ability to properly identify rib location with palpation. In fact, a recent case report outlines a pneumothorax caused by an extremely experienced practitioner inserting a needle into the rhomboid (Cummings 2014). Use of an electromyography (EMG) needle for trigger point injection has also been described to help limit the danger of pneumothorax (Botwin 2007). Additionally, ultrasound has been used as a modality to identify safe needling of the diaphragm (Amirjani 2012).

Electromyographers frequently need to insert a needle into the same muscles. The rhomboid major, which is innervated by the dorsal scapular nerve, is one of just a few muscles that is innervated almost exclusively by the C5 nerve root, which can help differentiate levels of a nerve root lesion. For the same reasons as dry needling, improper needle placement of an EMG needle can cause a pneumothorax.

When performing dry needling or EMG of the rhomboid major muscle, proper identification of the ribs provides an anatomic landmark to prevent needle insertion into the pleural space (Seol 2014, Travell/Simons). The technique is often called “blocking,” where the practitioner places the index finger in the intercostal space above or below a rib, with the middle finger on the intercostal space on the other side of the rib. This theoretically means that if a needle is inserted too deeply, it will only hit the rib and not go into the intercostal space. However, to our knowledge, this has never been investigated. Anecdotally, this is difficult to perform on someone with a large body habitus.

Objective:

1. Identify the accuracy of palpation guided identification of the ribs underlying the rhomboid major muscles.
- 2.

Subjects to study:

Inclusion criteria:

Adults >18 years old

Main exclusion criteria:

Prior surgery or scarring to the posterior aspect of the shoulder, which will make accurate localization of the rib using ultrasound difficult.

Methodology:

Subjects will be identified using inclusion criteria and consented. No personally identifiable patient information will be collected. The subject’s age, height, weight, and gender will be recorded. The patient will be positioned in the prone or seated position, as per the practitioner’s usual custom. The practitioner will then palpate to identify a posterior rib location under the rhomboid major. They will then place a single dot over what they perceive as the midline of the rib using a felt tip, skin-marking pen.

A second practitioner, trained in ultrasound identification, will then use a linear probe on an ultrasound machine to obtain a clear view of the ribs in a perpendicular alignment over the placed skin marking. The linear probe has a line signifying the middle of the probe, which will be placed directly over the center of the skin marking. This will be done with the rib in short axis to the ultrasound probe. Images will be saved for review, and will be analyzed for skin-to-rib depth as well as the rib location (e.g. middle 50%, outer 25% of the rib).

Data management and analysis:

Data will be collected in an Excel spreadsheet file. As there will be no personally-identifiable information contained, it will not be password-protected. Our primary outcome will be a simple percentage of accurate vs. inaccurate rib identifications. Secondly, data will be examined for normality by Kolmogorov-Smirnov testing. Logistic regression testing will be used to examine a relationship between BMI & accuracy and between depth & accuracy.

Sample size needed for the study:

As no data has been published on this study, we are using clinical opinion. Anecdotally, we feel that on patients with a normal BMI, the inaccuracy rate will be almost zero. However, in obese subjects, this value is probably much larger. We would estimate that 10% of overweight individuals would have inaccurate readings. For a p value of 0.05, this would require 46 overweight subjects. If we make the assumption that half of subjects are overweight, we should recruit 92 total subjects.

Ethical considerations:

Recruitment plans: Participants will be recruited for participation from patients in our musculoskeletal clinics at the University of Utah.

Compensation: None

Risks of the study: There is minimal risk associated with participation in the study. There is a very low risk of a local reaction to the skin-marking ink or ultrasound gel.

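### Probe placement over the ink dot cannot be verified, so its error cannot be separated from palpation error in the primary accuracy percentage

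*Combined protocol and SAP*

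**What the plan says.** All of this is in the protocol's Methodology section unless noted.

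- **Position.** "The patient will be positioned in the prone or seated position, as per the practitioner’s usual custom". Nothing further is said about position, arm placement or breathing.
- **Mark.** After palpating: "They will then place a single dot over what they perceive as the midline of the rib using a felt tip, skin-marking pen".
- **Scan.** "A second practitioner, trained in ultrasound identification, will then use a linear probe on an ultrasound machine". The view is to be perpendicular, with the rib in short axis.
- **Registration.** "The linear probe has a line signifying the middle of the probe, which will be placed directly over the center of the skin marking". No tolerance, reference line, image-visible marker, photograph or repeat placement is described.
- **Reading.** Images are saved for later review and read for skin-to-rib depth and for "rib location (e.g. middle 50%, outer 25% of the rib".
- **Gel.** Its use appears only under Ethical considerations: "There is a very low risk of a local reaction to the skin-marking ink or ultrasound gel".

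Under Data management and analysis, the primary outcome is the percentage of accurate versus inaccurate identifications, and logistic regression relates accuracy to BMI and to depth. The sample size section expects inaccuracy close to zero at normal BMI and about 10% in overweight subjects.

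**The concern.** The study measures the palpator's error, but it observes that error plus the error of setting the probe over the dot. A linear probe placed on a dot covers it, so the operator must judge the last millimetres without seeing the target. A later reader of the saved image can measure the rib, but cannot confirm that the image centre was the dot. If the subject shifts between marking and scanning, that also enters the reading.

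This matters because the expected error rates are low. When nearly all marks are truly on the rib, added random error mostly moves marks off it, and the study would report palpation as less accurate than it is. The BMI and depth regressions use the same outcome, so they carry the same error.

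**Working it through.** **The plan's own figure.** The plan gives no figure for alignment error or rib width, so there is nothing to reproduce on this point. Its only calculation, 46 / 0.5 = 92 subjects, is arithmetically right and does not bear on the matter.

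**Inputs**

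- True inaccuracy p: 10% in overweight subjects (sample size section). The plan gives close to zero at normal BMI; 1% is assumed here to represent it.
- Rib width W: 10, 12 and 15 mm (assumed).
- Alignment error: independent of palpation error, normal, mean zero, SD e = 1, 2 or 3 mm (assumed).
- Palpation error: normal, mean zero (assumed).
- Hit: the mark lies anywhere on the rib (assumed, because the plan does not tie accuracy to a band of the rib).

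**Formulas**

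- Palpation SD: s = (W/2) / z, where z is the upper p/2 point of the standard normal.
- Observed inaccuracy: 2 × [1 − Φ((W/2) / √(s² + e²))].

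**Worked case, W = 12 mm, e = 2 mm**

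- True 1%: s = 6 / 2.576 = 2.33. √(2.33² + 2²) = 3.07. 6 / 3.07 = 1.95. Observed 5.1%.
- True 10%: s = 6 / 1.645 = 3.65. √(3.65² + 2²) = 4.16. 6 / 4.16 = 1.44. Observed 14.9%.

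**Across the assumed range**

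| Rib width | Alignment SD | True 1% reads as | True 10% reads as | Difference (true 9.0 points) | Odds ratio (true 11.0) |
|---|---|---|---|---|---|
| 10 mm | 1 mm | 2.2% | 11.8% | 9.6 | 6.0 |
| 10 mm | 2 mm | 7.3% | 16.9% | 9.7 | 2.6 |
| 10 mm | 3 mm | 16.2% | 24.2% | 8.0 | 1.7 |
| 12 mm | 1 mm | 1.8% | 11.3% | 9.5 | 7.0 |
| 12 mm | 2 mm | 5.1% | 14.9% | 9.9 | 3.3 |
| 12 mm | 3 mm | 11.4% | 20.4% | 9.0 | 2.0 |
| 15 mm | 1 mm | 1.5% | 10.8% | 9.3 | 8.1 |
| 15 mm | 2 mm | 3.4% | 13.2% | 9.8 | 4.4 |
| 15 mm | 3 mm | 7.3% | 16.9% | 9.7 | 2.6 |

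The true odds ratio is (0.10/0.90) / (0.01/0.99) = 11.0. It compares two groups and stands in for the planned regression on BMI.

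**Direction of the switches (12 mm, SD 2 mm)**

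- True 1%: 4.4% of subjects go from hit to miss and 0.4% from miss to hit.
- True 10%: 7.6% go from hit to miss and 2.7% from miss to hit. So 2.7 / (7.6 + 2.7) = 26% of switches go the favourable way.

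**Sensitivity to the baseline (12 mm, SD 2 mm).** A true 0.1% reads as 2.7% and a true 0.5% as 4.0%, against 5.1% for a true 1%.

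**Tilt (conditional).** A tilt shifts the point under the probe centre by depth × tan(angle). At an assumed 5 degrees this is 1.3 mm at 15 mm depth and 2.6 mm at 30 mm. Taken as the alignment SD with a 12 mm rib, those shifts turn the same true 1% into 2.5% and 8.7%.

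**The case against.** Alignment is not left uncontrolled. The plan names a trained operator, a centre-line rule and a perpendicular short-axis view. That stands: what is missing is verification, not a rule. The perpendicular view may also limit tilt, although it may only mean perpendicular to the rib, and no tolerance is given. The depth argument is therefore conditional on some tilt remaining.

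A reader might infer that posture changes between marking and scanning. The documents do not support that. The text runs straight from positioning to marking to scanning and mentions no move; it simply does not require the position to be held. Likewise, no sentence says that the dot is hidden or that the image lacks a marker. The first follows from putting a probe on top of a dot; the second is only silence about any marker.

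A reader might also infer that every alignment error counts against the palpator, or that the contrast between BMI groups is lost. Neither holds. About a quarter of switches at a true 10% (12 mm, SD 2 mm) turn misses into hits, and the absolute difference stays at 8.0–9.9 points against a true 9.0. Only ratio measures shrink.

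Finally, the size is assumed. At SD 1 mm with a 12 mm rib, 10% becomes 11.3%, which is small beside a sampling standard error of √(0.1 × 0.9 / 46) = 4.4 points. That is fair for the overweight group. It is weaker at normal BMI, where the rate nearly doubles even at 1 mm.

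**Conclusion.** The point holds as a gap in verification. The primary percentage combines palpation error with probe-placement error, and the plan provides no means of telling them apart.

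Over the assumed range (ribs 10–15 mm, alignment SD 1–3 mm, normal independent errors, hit anywhere on the rib), a true 1% would read as about 1.5–16% and a true 10% as about 11–24%. The net bias is toward overstating inaccuracy. The odds ratio between the groups falls from 11.0 to between 8.1 and 1.7, with little change in the absolute difference. Residual tilt, if there is any, would add error that grows with depth, which is a tested predictor.

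The documents cannot show where in this range the study lies. That the effect could be anything from negligible to dominant is the reason to control it, since unverified placement cannot be recovered from the saved images afterwards.

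**What to change.** Add a few sentences to Methodology:

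1. After the dot is placed and before gel is applied, draw short skin lines through its centre, for example a small cross, long enough to reach past the probe's edges.
2. Align the housing midline to these lines, which stay visible during the scan. If the true short-axis view needs a different angle, rotate the probe about the dot. The lines are drawn before the rib is seen, so they should fix the dot's position and not dictate the rib's direction.
3. Save the image with the on-screen centre line shown, so that the reader scores at a defined point.
4. Scan directly after marking, in the same position and with the arms unmoved.

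This uses the same pen and machine and takes a few seconds per subject. The downside is that the two practitioners must follow each other directly. The lines reduce alignment error but do not measure it. If its size is wanted, the probe could be lifted and re-placed in a subset, at the cost of a second image for those subjects.
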